4.1.2. Secondary

- To assess the PK exposures of PF-06252616 in LGMD2I.
- To evaluate the PD activity of PF-06252616 based on the percent change of muscle volume as measured on MRI compared to baseline.
- To evaluate the PD activity of PF-06252616 based on GDF-8 (myostatin) modulation in blood and in tibialis muscle.
- To characterize the functional effects of PF-06252616 on muscle strength and functional assessments compared to baseline.
- To characterize the effects of PF-06252616 on respiratory function compared to baseline.

- To characterize the effects of PF-06252616 on Patient reported outcome measures.
- To evaluate the immunogenicity of PF-06252616.

4.1.3. Exploratory

• To evaluate functional outcome measures in LGMD2I.

4.2. Endpoints

4.2.1. Primary Safety

- Incidence of dose limiting or intolerability treatment related AEs by day 337 or 561.
- Incidence, severity and causal relationship of treatment emergent AEs (TEAEs) and withdrawals due to TEAEs by day 337 or 561.
- Incidence and magnitude of abnormal laboratory findings (clinical laboratory tests [hematology, chemistry], GGT, GLDH, PT, aPTT, creatine kinase, amylase, serum ferritin, serum iron, % transferrin saturation, Total Iron Binding Capacity (TIBC), LH, FSH, estrogen, cardiac troponin I, fecal occult blood and urinalysis) by day 337 or 561.
- Abnormal and clinically relevant changes in liver MRI and physical examinations, weight, vital signs, ECG, echocardiogram measured LVEF, DXA (bone mineral density), menstruation cycle as monitored by diary and C-SSRS (See Appendix 1 And Appendix 2 of the protocol) parameters by day 337 or 561.

4.2.2. Secondary Endpoints

4.2.2.1. Pharmacokinetic

• All subjects receiving active drug: serum PF-06252616 C_{max} and C_{trough} for all visits with PK collections and at steady-state.

4.2.2.2. Pharmacodynamic

- Mean percent change from baseline in muscle volume as measured on MRI.
- Total serum GDF-8 concentrations for all visits with GDF-8 collections

4.2.2.3. Strength and Function

- Mean change from baseline on function tests including PUL, Timed up-and-go (TUG), 10-meter walk/run (10MR), 2-meter walk test (2MWT), and 4 stair climb (4SC).
- Mean change from baseline on pulmonary function tests including forced vital capacity (FVC), FEV1(forced expiratory volume in 1 second), maximal inspiratory pressure (MIP) and maximal expiratory pressure (MEP).

• *Mean change from baseline on muscle strength by manual muscle test (MMT) and Hand-Held dynamometry.*

4.2.2.4. Patient Reported Outcomes

• Mean change from baseline on Patient reported outcomes (InQoL, SF-36)(See Appendix 3 and Appendix 4 of the protocol).

4.2.2.5. Immunogenicity

• *Incidence of ADA and NAb development.*

4.2.3. Exploratory Endpoint

4.2.3.1. Pharmacologic

- *Mean percent change from baseline in lean body mass by DXA.*
- *Mean percent change from baseline in muscle quality (fat infiltration) as measured by quantitative Dixon.*
- Mean change from baseline in muscle quality as measured by T1/STIR.

4.2.3.2. Function

• Evaluate the utility and changes from baseline of Functional Workspace as an outcome measure for LGMD2I.

5. ANALYSIS SETS

5.1. Full Analysis Set

All analyses will be based on the full analysis set (FAS) which includes all enrolled subjects who have received at least one dose of study drug.

5.2. Safety Analysis Set

Safety analyses will be based on the full analysis set.

5.3. Other Analysis Sets

5.3.1. PK Concentration Analysis Set

The PK concentration population is defined as all enrolled subjects who received at least 1 dose of PF-06252616 and in whom at least 1 concentration value is reported.

5.3.2. GDF-8 Concentration Analysis Set

The GDF-8 concentration population is defined as all enrolled subjects in whom at least 1 concentration value is reported.

6. ENDPOINTS AND COVARIATES

6.1. Safety Endpoints

Safety data will be summarized according to current Pfizer data standards including incidence of anti-drug antibodies and neutralizing antibodies by days 1 (to capture low dose safety) and 561 (last visit) for cohort 1 and day 337 (last visit) for cohorts 2 and 3.

At the screening visit, the "Baseline/Screening" assessment from the Columbia Suicide Severity Rating Scale will be performed. At all other visits the "Since Last Visit" assessment will be performed. The score at the screening visit will be the baseline. All adverse events will be reported under the treatment last received prior to the onset of the adverse event.

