## Cohort 3 (n=8):

- Lead-in period (16 weeks)
- Treatment: PF-06252616 40 mg/kg (32 weeks)
- Follow-up period (16 weeks)
- Extension period: PF-06252616 40 mg/kg (24 weeks)

[figure not shown]
At each dose level, subjects will be followed for an initial approximate 16-week lead-in period to establish individual change in disease progression.

The study will begin with 4 subjects being enrolled into Cohort 1. Following the lead-in period, subjects in Cohort 1 will be dosed with 5 mg/kg for a total of 32 weeks (8 doses). Cohort 2 will begin dosing at the mid dose level (20 mg/kg) once safety has been confirmed with subjects in Cohort 1 who have been treated for 16 weeks. Cohort 1 and 3 will begin dosing at the highest dose level (40 mg/kg) once safety has been confirmed with subjects in Cohort 2 who have been treated for 16 weeks.

Each dose level will be evaluated for 32 weeks (8 doses each). Cohort 1 is the only cohort who will receive 2 dose levels (5 mg/kg and 40 mg/kg) and their total treatment time will be a minimum of 64 weeks. Subjects in Cohort 1 will only receive 8 doses of the 5 mg/kg dose and not proceed to the 40 mg/kg dose until safety review and approval by the SMC.

At the conclusion of the treatment period, subjects will be followed for an additional 16 weeks to monitor for safety, PK and duration of response.

All subjects completing the follow-up period will have the option to continue treatment with 40mg/kg dose in the Extension Period.

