### 3.5. Safety Monitoring and Dose Escalation

Safety monitoring will be conducted by the Investigator, Pfizer Medical Monitor and an External Medical Monitor. This group will be referred to as the Safety Monitoring Committee (SMC). Safety monitoring by these individuals will include the following reviews:

- Dose escalation
- Quarterly safety and
- Ad hoc safety

At each review, a consideration will be made of the number of subjects who have severe AEs or serious AEs in the same organ system which are determined to be related to investigational product. The SMC may determine it is necessary to close or adjust a dose level within the study. The first dose escalation decision, whether or not to increase from 5 mg/kg in Cohort 1 to 20 mg/kg in Cohort 2 will occur after review of all safety data after the 4th subject of Cohort 1 has completed the planned 16 weeks (day 85) or 4 doses. The second dose escalation decision, whether or not to increase from 20 mg/kg in Cohort 2 to 40 mg/kg in Cohorts 1 and 3 will occur after the 4th subject in Cohort 2 had completed the planned 16 weeks (day 85) or 4 doses. A break in dosing of subjects in Cohort 1 between 5 mg/kg and 40 mg/kg may occur to ensure all safety data from Cohort 2 at 20 mg/kg has been evaluated by the SMC. Should a break be required in Cohort 1 between Day 197 and 225 ( $\pm$ 3 days) which is longer than the planned 28 days between dosing visits and outside the visit schedule, the window will not be applied. When the dosing resumes in Cohort 1 at the highest dose, the first day of dosing will be Visit 11 and the remaining dosing schedule will follow the Schedule of Activities, whereby dosing will occur every 28 days ( $\pm$  3 days).

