## **5. STUDY TREATMENTS**

Subjects will be treated with IV infused PF-06252616 in this open-label, multiple ascending dose study. Please refer to the Dosing and Administration Instruction (DAI) for complete information on storage, stability, preparation and administration of drug product (PF-06252616).

Study Visit Day	1	29	57	85	113	141	169	197
Cohort 1				5mg/kg onc	e every 4 we	eks		
Study Visit Day	225	253	281	309	337	365	393	421
Cohort 1	I			40 mg/kg on	ce every 4 w	reeks		
Study Visit Day	589	617	645	673	701	729	757	
Cohort 1		EXTE	NSION PEF	RIOD : 40 mg	g/kg once ev	ery 4 weeks	1	

### Table 3.Dosing Schedule for Cohort 1

#### Table 4.Dosing Schedule for Cohort 2 and 3

Study Visit Day	1	29	57	85	113	141	169	197		
Cohort 2	20 mg/kg once every 4 weeks									
Study Visit Day	365	393	421	449 4	77 505	533	561	589		
Cohort 2	EXTENSION PERIOD: 40 mg/kg once every 4 weeks									
Study Visit Day	1	29	57	85	113	141	169	197		
Cohort 3	40 mg/kg once every 4 weeks									
Study Visit Day	365	393	421	449	477	505				
Cohort 3		EXTENSI	ON PERIC	))): 40 mg/l	g once every	4 weeks				

This study is a 3 cohort clinical trial. In a dose escalating fashion, subjects will be enrolled in one of 3 cohorts and will receive treatment on a 28 day schedule, per the Schedule of Activities. The dose will be dependent on the cohort and calculated based on the subject weight at each visit prior to each infusion.

Subjects in Cohort 1 will receive treatment with 5 mg/kg of PF-06252616 for 32 weeks and after safety and tolerability review of Cohort 1 subjects receiving 5 mg/kg and Cohort 2 subjects receiving 20 mg/kg will be escalated to 40 mg/kg of PF-06252616 for an additional 32 weeks. Subjects in Cohort 2 will receive treatment with 20 mg/kg of PF-06252616 for 32

weeks. Subjects in Cohort 3 will receive treatment with 40 mg/kg of PF-06252616 for 32 weeks. Subjects who completed the Follow-up period and opt to continue in the Extension period will receive treatment with 40mg/kg of PF-06252616 for up to 28 weeks in Cohort 1 and up to 40 weeks in Cohort 2, and 24 weeks in Cohort 3.

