#### **Prior to dosing, the following procedures will be completed:**

- Physical Examination, including Nose and Throat Mucosal Exam
- **Pregnancy Test**: A highly sensitive urine pregnancy test will be performed on all female subjects
- Diary Cards: For collection of first day of each menstrual cycle for WOCBP.
- Contraception Review: Confirmation of use of acceptable forms of contraception
- Weight
- Vital signs: Supine blood pressure, pulse rate, respiratory rate, and oral temperature.
- **12-lead ECG:** ECGs will be performed in triplicate
- Clinical laboratory tests:
  - Hematology with complete blood count and differential, comprehensive metabolic panel (sodium, potassium, chloride, carbon dioxide, blood urea nitrogen, creatinine, calcium, glucose, total protein, albumin, total bilirubin, AST, ALT, alkaline phosphatase) gamma-glutamyl transferase (GGT), prothrombin time (PT), activated partial thromboplastin time (aPTT), creatine kinase, amylase, cardiac troponin I. Urinalysis.
- Serum ferritin, serum iron, % transferrin saturation, TIBC: fasting blood collection
- Horomone Testing: LH, FSH, estrogen in WOCBP
- GLDH
- **Fecal occult blood**: Fecal sample is to be collected at home within 1 week prior to scheduled visit.
- C-SSRS

- Immunogenicity: Baseline
- PD sample collection: Predose
- PK sample collection: Predose
- **MRI-liver**: Liver MRI will be obtained for iron accumulation (visit 11 only)
- **MRI-muscle:** WB-MRI and dedicated thigh MRI will be performed for muscle quantity and quality
- **DXA Whole Body:** Whole body DXA will be performed for lean body mass.
- **DXA Spine and Hip:** Spine and hip DXA will be performed for BMD.
- **Functional assessments:** Must be conducted in the following order: Respiratory function (FVC, FEV1, MIP, MEP), 4SC, 2MWT, 10-meter walk/run, TUG, strength assessment (MMT, hand-held dynamometry) and PUL.
- Quality of Life assessments
  - InQol
  - SF-36

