- **Pregnancy Test**: A highly sensitive urine pregnancy test will be performed on all female subjects
- **Diary Card:** For collection of first day of each menstrual cycle for WOCBP.
- Contraception Review: Confirmation of use of acceptable forms of contraception
- Vital signs: Supine blood pressure, pulse rate, respiratory rate, and oral temperature.
- 12-lead ECG: ECGs will be performed in triplicate
- Echocardiogram
- Clinical laboratory testing:
  - Hematology with complete blood count and differential, comprehensive metabolic panel (sodium, potassium, chloride, carbon dioxide, blood urea nitrogen, creatinine, calcium, glucose, total protein, albumin, total bilirubin, AST, ALT, alkaline phosphatase) gamma-glutamyl transferase (GGT), prothrombin time (PT), activated partial thromboplastin time (aPTT), creatine kinase, amylase, cardiac troponin I. Urinalysis.

- Serum ferritin, serum iron, % transferrin saturation, TIBC: fasting blood collection
- Horomone Testing: LH, FSH, estrogen in WOCBP
- GLDH
- **Fecal Occult Blood:** Fecal sample is to be collected at home within 1 week prior to scheduled visit.
- C-SSRS
- **MRI-liver**: Liver MRI will be obtained for iron accumulation
- **MRI-muscle:** WB-MRI and dedicated thigh MRI will be performed for muscle quantity and quality
- **DXA Whole Body:** Whole body DXA will be performed for lean body mass assessment.
- **DXA Spine and Hip:** Spine and hip DXA will be performed for BMD.
- **Functional assessments:** Must be conducted in the following order: Respiratory function (FVC, FEV1, MIP, MEP), 4SC, 2MWT, 10-meter walk/run, TUG, strength assessment (MMT, hand-held dynamometry), and PUL.
- **Needle muscle biopsy:** Following WB-MRI and functional assessments, a needle muscle biopsy of the tibialis muscle will be performed.
- Quality of Life assessments
  - InQol
  - SF-36
- Immunogenicity sample collection.
- PD sample collection
- PK sample collection
- Adverse Event monitoring
- Infusion site reaction
- Concomitant medication

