2.1. Study Design

This is a Phase 1b/2, open-label multiple ascending dose study to evaluate the safety, tolerability, efficacy, PK and PD of PF-06252616 administered to in ambulatory participants diagnosed with LGM21. Three IV infused dose levels administered every 28 days will be investigated in a dose escalating fashion.

PF-06252616 dose levels:

- 5 mg/kg.
- 20 mg/kg.
- 40 mg/kg.

Approximately 20 eligible subjects will be consecutively assigned to 1 of 3 cohorts for approximately 96 weeks (cohort 1) or 64 weeks (cohorts 2 and 3).

Cohort 1 (n=4):

- Lead-in period (16 weeks)
- *Treatment A: PF-06252616 5 mg/kg (32 weeks)*
- Treatment B: PF-06252616 40 mg/kg (32 weeks)
- Follow-up period (16 weeks)

Cohort 2 (n=8):

- Lead-in period (16 weeks)
- Treatment: PF-06252616 20 mg/kg (32 weeks)
- Follow-up period (16 weeks)

Cohort 3 (n=8):

• Lead-in period (16 weeks)

[figure not shown]
- Treatment: PF-06252616 40 mg/kg (32 weeks)
- Follow-up period (16 weeks)

At each dose level, subjects will be followed for an initial 16-week lead-in period to establish individual change in disease progression.

The study will begin with 4 subjects being enrolled into Cohort 1. Following the lead-in period, subjects in Cohort 1 will be dosed with 5 mg/kg for a total of 32 weeks (8 doses). Cohort 2 will begin dosing at the mid dose level (20 mg/kg) once safety has been confirmed with subjects in Cohort 1 who have been treated for 16 weeks. Cohort 1 and 3 will begin dosing at the highest dose level (40 mg/kg) once safety has been confirmed with subjects in Cohort 2 who have been treated for 16 weeks.

Each dose level will be evaluated for 32 weeks (8 doses each). Cohort 1 is the only cohort who will receive 2 dose levels (5 mg/kg and 40 mg/kg) and their total treatment time will be 64 weeks.

At the conclusion of the treatment period, subjects will be followed for an additional 16 weeks to monitor for safety, PK and duration of response.

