8.2.1.7. Immunogenicity

Immunogenicity analysis will be based on the immunogenicity analysis population which will be the same as the safety analysis population. This will include anti-drug antibody and neutralizing antibody development by all visits with ADA samples until the end of follow-up. Both continuous endpoints (titer) and categorical endpoints (i.e. positive, negative and inconclusive) will be reported for the anti-drug antibody and neutralizing antibody assays by dose and sampling time points. Data permitting, the incidence of anti-drug antibody and neutralizing antibody will be summarized by time points within each dose cohort and may be also summarized by dose. The impact of anti-drug antibody and neutralizing antibody on PK and PD parameters and profiles, efficacy and safety may be also evaluated but no formal statistical inference will be drawn.

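### SAP 6.1 takes Cohort 1's low-dose anti-drug antibody result from Day 1, which is the pre-dose baseline; its last-visit label also overlooks the protocol's optional extension

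*SAP*

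**What the plan says.** **Antibody time points.** SAP 6.1 (Safety Endpoints) requests "incidence of anti-drug antibodies and neutralizing antibodies by days 1 (to capture low dose safety) and 561 (last visit) for cohort 1", and Day 337, also labelled as the last visit, for Cohorts 2 and 3. SAP 8.2.1.7 sets a different scope: "This will include anti-drug antibody and neutralizing antibody development by all visits with ADA samples until the end of follow-up". It reports titre and positive, negative or inconclusive status by dose and sampling time. Incidence by time point within each cohort follows if the data allow.

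**When the samples are taken.** Protocol 6.3 covers Visit 3 (Day 1) and, for Cohort 1, Visit 11 (Day 225). Its list of procedures to be done before dosing includes "Immunogenicity: Baseline". The Cohort 1 Schedule of Activities marks immunogenicity in the column shared by Visits 3 and 11, at Visits 19 and 20, and at Early Withdrawal. Protocol 6.15 lists "Immunogenicity sample collection" among the assessments that may be done at an early withdrawal visit.

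**Extension.** Protocol 3.1 states: "All subjects completing the follow-up period will have the option to continue treatment with 40mg/kg dose in the Extension Period". Protocol 5 gives the length as "up to 28 weeks in Cohort 1 and up to 40 weeks in Cohort 2, and 24 weeks in Cohort 3". The SAP design section (2.1) ends with the 16-week follow-up, and the SAP text available for review does not mention an extension.

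**The concern.** The antibody summary at Day 1 is meant to isolate what happens at 5 mg/kg before Cohort 1 moves to 40 mg/kg. A sample drawn before any drug is given shows only pre-existing reactivity. Anyone who follows 6.1 literally would present baseline status as the low-dose result, and anyone who follows 8.2.1.7 would present something else. Incidence of anti-drug and neutralizing antibodies is a listed secondary endpoint, so the SAP should give one answer.

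The same sentence of 6.1 calls Days 561 and 337 the last visit. Under the current protocol these days end the main-study follow-up, and subjects may then receive further 40 mg/kg infusions with further safety sampling. The SAP gives no statement on how the laboratory, vital sign, liver R2* and antibody data from that period are to be presented.

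**Working it through.** **Step 1. Doses before each candidate sample (Cohort 1).** Protocol 5, Table 3, puts the 5 mg/kg doses on Days 1 + 28 × i for i = 0 to 7: Days 1, 29, 57, 85, 113, 141, 169 and 197. Count the doses given before a pre-dose sample on each day:

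- Day 1 (Visit 3): 0 of 8.
- Day 225 (Visit 11; 1 + 8 × 28 = 225): 8 of 8, and none at 40 mg/kg.

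The SAP says by, not at, Day 1. The count is 0 on either reading. The pre-dose list in protocol 6.3 serves both visits, so its baseline label is printed once for both; only at Visit 3 does the sample precede all drug.

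**Step 2. Which samples can answer the low-dose question.** Each Cohort 1 subject has at most one scheduled sample after 5 mg/kg and before 40 mg/kg. It is either Visit 11 pre-dose or, for a subject who leaves during 5 mg/kg, the Early Withdrawal sample if one is taken. Visits 19 and 20 follow 40 mg/kg. With 4 subjects that makes up to 4 informative samples, and the Day 1 time point contains none of them.

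**Step 3. Why a visit and not a day.** Protocol 3.5 allows a dosing break before escalation. It then states that "the first day of dosing will be Visit 11 and the remaining dosing schedule will follow the Schedule of Activities". Visit 11 can therefore fall later than Day 225, and a rule fixed to Day 225 could miss it.

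**Step 4. How far the extension runs past the labelled last visit.** Scheduled dosing days come from protocol 5, Tables 3 and 4.

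- Cohort 1: last extension dose on Day 757; 757 − 561 = 196 days later.
- Cohort 3: Day 505; 505 − 337 = 168 days later.
- Cohort 2: Table 4 as it appears here prints nine days, ending on Day 589 (589 − 337 = 252 days). The Cohort 2 extension schedule has ten dosing visits; the tenth on a 28-day grid is 365 + 9 × 28 = Day 617 (617 − 337 = 280 days). The two sources need reconciling, so both counts are carried below.

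**Step 5. Size of the extension at 40 mg/kg, with full uptake and no missed doses.**

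- Main study: 4 × 8 (Cohort 1) + 8 × 8 (Cohort 3) = 96 infusions.
- Extension, ten Cohort 2 visits: 4 × 7 + 8 × 10 + 8 × 6 = 28 + 80 + 48 = 156. Share: 156 / (96 + 156) = 156/252 = 61.9%.
- Extension, nine Cohort 2 days: 28 + 72 + 48 = 148. Share: 148 / (96 + 148) = 148/244 = 60.7%.
- Final extension antibody samples (Visits 27, 22 and 18): up to 4 + 8 + 8 = 20.

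**The case against.** The strongest reply is that 6.1 is a one-sentence description and 8.2.1.7 is the operative analysis. It covers all antibody visits, by dose and sampling time, and the planned antibody table is by dose level. This stands. A reader might infer that a subject who converts at 5 mg/kg would go unreported. The documents do not support that, because Visit 11 is tabulated under 8.2.1.7. What remains is a wrong rule in 6.1 and a conflict between sections.

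Several stronger readings of the extension point are also tempting and do not hold:

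- **That extension safety data have no grouping rule at all.** SAP 6.1 assigns each adverse event to the most recent treatment before onset. The planned adverse event tables and the laboratory abnormality incidence table include versions by dose level and cohort. The gap is mainly in the other safety data.
- **That the SAP departs from the protocol in saying** "Cohort 1 is the only cohort who will receive 2 dose levels (5 mg/kg and 40 mg/kg". The same sentence stands in protocol 3.1 beside the extension text. It sits badly with Cohort 2 moving from 20 to 40 mg/kg in the extension, but the tension is the protocol's own.
- **That 8.2.1.7 excludes the final extension antibody sample.** In the SAP's design, follow-up means the 16 weeks after treatment, but the current protocol also has a telephone follow-up after the extension. The wording is ambiguous.
- **That adverse event summaries for the complete study omit the extension.** Protocol 3.3 and 13 end the study at the last subject's last visit, which can include it. The SAP leaves this unsaid.
- **That repeated visit numbers will pool different exposure periods.** Visits 13 to 20 are main-study visits in Cohort 1 and extension visits in Cohort 2. Pooling would occur only if extension data entered tables arranged by visit number, and the SAP does not say that they do.

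The SAP's date relative to protocol Version 6 is unknown from the text available. It may have been written before the extension was added, which would explain the omission without filling it.

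**Conclusion.** The main point holds. Day 1 follows 0 of the 8 planned 5 mg/kg doses and cannot measure low-dose immunogenicity, and 6.1 disagrees with 8.2.1.7 about the same endpoint. The practical effect is small: one summary of a secondary endpoint in 4 subjects, with no data lost. This conclusion needs no assumption beyond the scheduled timing of the samples.

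The extension point holds in a narrow form. The last-visit label is wrong for any subject who enters the extension, and the SAP should say how that period's safety data other than adverse events are presented. The 61 to 62% share is a ceiling: it assumes the planned cohort sizes, full uptake and every dose given, and the documents do not state uptake. The Day 337 or 561 window for the primary safety endpoints is the same in SAP 4.2.1 and protocol 2.2.1 and is not in question.

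Both corrections should be made before the tables are produced.

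**What to change.** **SAP 6.1, antibodies.** Replace Day 1 as the low-dose time point with the last anti-drug and neutralizing antibody sample after the first 5 mg/kg dose and before any 40 mg/kg infusion. That is Visit 11 pre-dose (planned Day 225), or the Early Withdrawal sample if one is taken from a subject who leaves during 5 mg/kg. Keep Day 1 as baseline, and align 6.1 with 8.2.1.7 so that both name the same time points.

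**SAP 6.1, labels.** Call Days 561 and 337 the end of main-study follow-up. Leave the primary safety window unchanged.

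**Extension.** Describe the optional extension in SAP 2.1. State that its laboratory, vital sign, liver R2* and final antibody data are summarised separately by dose received and cohort. State in 8.2.1.7 that the final extension antibody sample is included, and in 8.2.1.1 whether the complete study covers the extension.

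**Cost.** These are SAP wording changes plus extra columns or separate tables for small groups. No new sample or visit is needed, since the antibody samples concerned are already in the protocol's schedules.
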